6.9.2 Esophagitis

Esophageal complaints are common with thoracic radiation therapy. Esophagitis does not constitute a reason to interrupt or delay radiotherapy provided oral intake is sufficient to maintain hydration. Patients should be advised to avoid alcoholic, acidic, or spicy foods or beverages. Viscous Xylocaine, Carafate, or other medications should be used for symptomatic relief. Occasionally, narcotics may be required.

It is not necessary to biopsy acute esophagitis in the first 2 weeks of therapy since it is rarely due to underlying viral or fungal disease. Acute esophagitis may persist for 4-6 weeks. If Grade 3 or 4 esophagitis occurs, and a treatment interruption is being considered, every effort should be made to limit it to 3 treatment days or less. Patients requiring hospitalization because of esophagitis may have their treatment interrupted. In this event, please notify [name].

Esophagitis should be graded according to the CTCAE v.4.0

Table 4. Esophagitis grading system

 	nagino grading oyotom
Grade	Clinical Scenario
1	Asymptomatic pathologic, radiographic, or endoscopic findings only
2	Symptomatic; altered eating/swallowing (e.g., altered dietary habits, oral
	supplements), IV fluids indicated <24 hrs
3	Symptomatic and severely altered eating/swallowing (e.g., inadequate oral
	caloric or fluid intake), IV fluids, tube feedings, or TPN indicated >24 hrs
4	Life-threatening consequences; urgent operative intervention indicated
5	Death

Treatment should be interrupted for grade 4 or greater dysphagia or odynophagia. Acute esophageal toxicity, which typically can occur within two weeks of the initiation of treatment and manifests as dysphagia, odynophagia, reflux symptoms, etc. should be pharmacologically managed with the following approach and should be initiated at the first signs or symptoms of esophageal toxicity. Recommended treatments are as follows:

- 1) Ketoconazole 200 mg PO q day OR Fluconazole 100 mg PO q day until the completion of radiation.
- 2) Mixture of: 2% viscous lidocaine: 60 cc, Mylanta: 30 cc, sucralfate (1 gm/cc): 10 cc; Take 15-30 cc PO q3-4 hrs prn. (Contraindications: pts on Dilantin, Cipro, Digoxin)
- 3) Ranitidine 150 mg PO BID (or other H2 blocker or a proton pump inhibitor such as omeprazole) until the completion of radiation
- 4) Grade 4 esophagitis: hold XRT until grade 2 or less. We expect a significant portion of patients will experience grade 3 esophagitis.

6.9.3 Pneumonitis

Radiation pneumonitis is a subacute (weeks to months from treatment) inflammation of the end bronchioles and alveoli. Note: It is very important that a Radiation Oncologist participate in the care of the patient, as the clinical picture may be very similar to acute bacterial

pneumonia, with fatigue, fever, shortness of breath, nonproductive cough, and a pulmonary infiltrate on chest x-ray. The infiltrate on chest x-ray should include the area treated to high dose, but may extend outside of these regions. The infiltrates may be characteristically "geometric" corresponding to the radiation portal, but may also be ill defined.

Patients reporting symptoms as above will be promptly evaluated and treated. Mild radiation pneumonitis may be treated with nonsteroidal anti-inflammatory agents or steroid inhalers. More significant pneumonitis will be treated with systemic steroids, bronchodilators, and pulmonary toilet. Supra- and concurrent infections should be treated with antibiotics. Consideration of prophylaxis of opportunistic infections should be considered in immunocompromised patients.

A suggested course of prednisone for both severe and moderate pneumonitis is shown below.

Prednisone comes in 1 mg. 2.5 mg. 5 mg. 10 mg. 20 mg. and 50 mg strength

RADI.		- PREDNISONE SCHEDUL	E
SEVERE PNE	UMONITIS	MODERATE PNEUMONITIS	
dose (mg)	days	dose (mg)	days
20 - 20 - 20	2	20 - 20 - 20	1
20 - 15 - 20	2	15 - 15 - 15	1
20 - 15 - 15	2	10 - 10 - 10	1
15 - 15 - 15	2	10 - 5 - 10	2
15 - 10 - 15	2	10 - 5 - 5	2
15 - 10 - 10	2	5 - 5 - 5	2
10 -10 - 10	2	5 - 2.5 - 5	3
10 - 5 - 10	2	5 - 2.5 - 2.5	3
10 - 5 - 5	2	2.5 - 2.5 - 2.5	3
5 - 5 - 5	2	2.5 - 2.5	4
5 - 2.5 - 5	3	2.5	4
5 - 2.5 - 2.5	3	2.5 qod	8
2.5 - 2.5 - 2.5	3	STOP	TOTAL = 34 days
2.5 - 2.5	4		
2.5	4		
2.5 qod	8		
STOP	TOTAL = 51 days		

For mild pneumonitis, consider non-steroidal treatment (e.g. 600-800 mg/day lbuprofen in divided doses) with or without an inhaled steroid (e.g. Vanceril or Azmacort 2 puffs qid).

Use H-2 blocker, H+ pump blocker, or Sucralfate for gastric prophylaxis.

Consider Bactrim (if not allergic) in severely immunocompromised patients to avoid opportunistic infection. Consider other appropriate antibiotics if cough is productive of greenish sputum or if clinical suspicion indicates bacterial supra-infection within the areas of pneumonitis.

If patient has return of pneumonitis symptoms during weaning of steroids, go back to dose level where patient was last comfortable and resume wean at that level. It may be necessary to lengthen interval at each dose (e.g. double from 3 to 6 days at a particular level) in order to successfully wean the patient. Be patient with steroid taper as patients may experience rebound pneumonitis if weaning proceeds too quickly.

Periodically check blood sugars, especially in obese patients or those with overt or borderline diabetes.

Properly performed incentive spirometry appears to help re-expand collapsed alveoli.

Excessive coughing should be treated with antitussives (e.g. Tessalon Perles 100 tid PRN).

Consider inhaled bronchodilator in patients who have signs of bronchospasm or reactive airways (e.g. Albuterol inhaler 2 puffs qid).

It is unlikely that symptomatic pneumonitis will occur during the weeks radiation is actually delivered to the patients. However, if a patient experiences pneumonitis before completing therapy, therapy will be put on hold until symptoms resolve. At that point, a clinical decision whether to finish therapy will be made in conjunction with the treating physician in conjunction with [name]. When symptomatic pneumonitis resolves to grade 0, CTCAE, v. 4.0, the treating physician will contact [name] for a decision to continue or terminate protocol therapy.

6.9.4 Changes in Pulmonary Function Tests

Patients enrolled to this study are allowed to have some degree of impaired pulmonary function as measured by pulmonary function tests (PFTs), including Forced Expiratory Volume in 1 second (FEV1), and Diffusing Capacity for Carbon Monoxide (DLCO). The Common Toxicity Criteria (CTCAE), v. 4.0 includes specified criteria for grading adverse events related to these PFT parameters under the category of pulmonary/upper respiratory. The grading criteria for these PFT changes use the "percent predicted" values from 0-100% which are recorded on the patient's PFT report. A percent predicted of 90% conveys that the patient is able to perform the PFT test to a result that is 90% of what would be expected for the normal general population of the same height, age, and sex. The CTCAE version 4 specified grading criteria for PFTs assumes that all patients have normal baseline pulmonary function. This assumption is not appropriate for this protocol enrolling patients with abnormal baseline function.

[figure not shown]
As a remedy to monitor treatment effects on PFTs, we will define a protocol specific toxicity classification for PFTs that adjusts for baseline abnormalities. Changes that occur after therapy will be referenced to the baseline for a given patient, which will be abnormal for most patients. We have defined a proportional decline from the baseline. Grade 1 toxicity will be a decline from baseline to a level 0.90 times the baseline, grade 2 will be a decline to a level 0.75 of baseline, grade 3 will be a decline to a level 0.5 of baseline, grade 4 will be a decline

[figure not shown]

to a level 0.25 of baseline, and grade 5 will be death. This scheme is depicted in the table below and graphically represented in the following figure.

As an example, a patient who enters the study with a percent predicted DLCO of 55% who experiences a post treatment decline to a percent predicted DLCO of 40% would have a grade 3 event in the original CTCAE version 4 criteria; however, under this modified PFT toxicity classification for patients with abnormal baseline, his decline would constitute a decrease to 0.72 of the baseline value which is between 0.75 and 0.5 or a grade 2 event.

The SBRT Pulmonary Toxicity Scale					
	Grade				
Adverse Event	1	2	3	4	5
FEV-1 Decline	0.90-0.75 times the patient's baseline value	<0.75-0.50 times the patient's baseline value	<0.50-0.25 times the patient's baseline value	<0.25 times the patient's baseline value	Death
Forced Vital Capacity Decline	0.90-0.75 times the patient's baseline value	<0.75-0.50 times the patient's baseline value	<0.50-0.25 times the patient's baseline value	<0.25 times the patient's baseline value	Death
DLCO Decline	0.90-0.75 times the patient's baseline value	<0.75-0.50 times the patient's baseline value	<0.50-0.25 times the patient's baseline value	<0.25 times the patient's baseline value	Death

6.10 Steps to Determine If a Serious Adverse Event Requires Expedited Reporting to the SCCC DSMC and/or HRPP

Step 1: Identify the type of adverse event using the NCI Common Terminology Criteria for Adverse Events (CTCAE v4).

Step 2: Grade the adverse event using the NCI CTCAE v4.

Step 3: Determine whether the adverse event is related to the protocol therapy. Attribution categories are as follows:

- Definite The AE is clearly related to the study treatment.
- Probable The AE is likely related to the study treatment.
- Possible The AE *may be related* to the study treatment.
- Unlikely The AE may NOT be related to the study treatment.
- Unrelated The AE is clearly NOT related to the study treatment.

Note: This includes all events to the end of the acute adverse events reporting period as defined in section 6.9.1. Any event that occurs during the late adverse event period as defined in section 6.9.1 and is attributed (possibly, probably, or definitely) to the agent(s) must also be reported as indicated in the sections below.

Step 4: Determine the prior experience of the adverse event. Expected events are those that have been previously identified as resulting from administration of the treatment. An adverse event is considered unexpected, for expedited reporting purposes only, when either the type of event or the severity of the event is not listed in:

- the current known adverse events listed in the Agent Information Section of this protocol (if applicable);
- the drug package insert (if applicable);
- the current Investigator's Brochure (if applicable)
- the Study Agent(s)/Therapy(ies) Background and Associated Known Toxicities section of this protocol

6.11 Reporting SAEs and UPIRSOs to the Simmons Comprehensive Cancer Center (SCCC) Data Safety Monitoring Committee (DSMC)

All SAE/UPIRSOs at all sites, which occur in research subjects on protocols for which the SCCC is the DSMC of record require reporting to the DSMC regardless of whether IRB reporting is required. All SAEs/UPIRSOs occurring during the protocol-specified monitoring period should be submitted to the SCCC DSMC within 5 business days of the PI or delegated study team members awareness of the event(s). In addition, for participating centers other than UTSW, local IRB guidance should be followed for local reporting of serious adverse events.

The UTSW study team is responsible for submitting SAEs/UPIRSOs to the SCCC DSMC Coordinator. Hardcopies or electronic versions of the eIRB Reportable Event report; FDA Form #3500A forms, or other sponsor forms, if applicable; and/or any other supporting documentation available should be submitted to the DSMC Coordinator. The DSMC Coordinator forwards the information onto the DSMC Chairman who determines if immediate action is required. Follow-up eIRB reports, and all subsequent SAE/UPIRSO documentation that is available are also submitted to the DSMC Chair who determines if further action is required. (See Appendix III of the SCCC DSMC Plan for a template Serious Adverse Event Form which may be utilized when a sponsor form is unavailable and SAE submission to the eIRB is not required).

If the event occurs on a multi-institutional clinical trial coordinated by the UTSW Simmons Comprehensive Cancer Center, the DOT Manager or lead coordinator ensures that all participating sites are notified of the event and resulting action, according to FDA guidance for expedited

reporting. DSMC Chairperson reviews all SAEs/UPIRSOs upon receipt from the DSMC Coordinator. The DSMC Chairperson determines whether action is required and either takes action immediately, convenes a special DSMC session (physical or electronic), or defers the action until a regularly scheduled DSMC meeting.

Written reports to:

UTSW Clinical Research Manager

Email: [contact]

UTSW Institutional Review Board (IRB)

Submit a Reportable Event via eIRB with a copy of the final sponsor report as attached

supporting documentation

Reporting Unanticipated Problems Involving Risks to Subjects or Others (UPIRSOs) to the UTSW HRPP/IRB

UTSW reportable event guidance applies to all research conducted by or on behalf of UT Southwestern, its affiliates, and investigators, sites, or institutions relying on the UT Southwestern IRB. Additional reporting requirements apply for research relying on a non-UT Southwestern IRB.

According to UTSW HRPP/IRB policy, UPIRSOs are incidents, experiences, outcomes, etc. that meet **ALL three (3)** of the following criteria:

- 1. Unexpected in nature, frequency, or severity (i.e., generally not expected in a subject's underlying condition or not expected as a risk of the study; therefore, not included in the investigator's brochure, protocol, or informed consent document), AND
- 2. Probably or definitely related to participation in the research, AND
- 3. Suggests that the research places subjects or others at a greater risk of harm (including physical, psychological, economic, or social harm) than was previously known or recognized. Note: According to OHRP, if the adverse event is serious, it would always suggest a greater risk of harm.

For purposes of this policy, UPIRSOs include unanticipated adverse device effects (UADEs) and death or serious injury related to a humanitarian use device (HUD).

UPIRSOs must be promptly reported to the UTSW IRB within 5 working days of PI awareness.

For research relying on a non-UT Southwestern IRB (external, central, or single IRB):

Investigators relying on an external IRB who are conducting research on behalf of UT Southwestern or its affiliates are responsible for submitting **LOCAL** UPIRSOs to the UT Southwestern IRB within 5 working days of PI awareness. Investigators must report to their relying IRB according to the relying IRB's policy. In addition, the external IRB's responses or determinations on these local events must be submitted to the UT Southwestern IRB within 10 working days of receipt.

Events NOT meeting UPIRSO criteria:

Events that do NOT meet UPIRSO criteria should be tracked, evaluated, summarized, and submitted to the UTSW HRPP/IRB at continuing review.

For more information on UTSW HRPP/IRB reportable event policy, see

https://www.utsouthwestern.edu/research/research-administration/irb/assets/policies-combined.pdf.

7.0 Drug Therapy

At the treating physician's discretion, chemotherapy may be administered concurrently ONLY to patients enrolled on the standard arm (30 fractions) using a combination of carboplatin and paclitaxel (Taxol) with standard dosing for concurrent chemo-radiotherapy in lung cancer. Patients treated on this arm, however, may not receive any other chemotherapy regimens, targeted therapy, or drugs known to act as radiosensitizers. Patients on the experimental arm (15 fractions) may NOT receive any concurrent chemotherapy, targeted therapy or drugs known to act as radiosensisitizers. Patients on either arm of the study may go on to receive adjuvant chemotherapy if determined appropriate by their medical oncologist one week after completing radiation therapy.

8.0 Permitted Supportive Therapy

All supportive therapy for optimal medical care will be given during the study period at the discretion of the attending physician(s) within the parameters of the protocol and documented on each site's source documents as concomitant medication.

- **8.1** Antiemetics
- **8.2** Anticoagulants
- **8.3** Antidiarrheals
- 8.4 Analgesics
- 8.5 Hematopoietic Growth Factors
- **8.6** Herbal products
- 8.7 Nutritional supplementation

9.0 Patient Assessments

9.1 Study Parameters: Please see Appendix II for the patient assessment schedule. Patients will be followed until death.

9.2 Criteria for Toxicity

All acute and late adverse events from protocol radiation therapy will be reported and scored for severity using the NCI Common Terminology Criteria for Adverse Events (CTCAE) version 4.0. A copy of the CTCAE v4.0 can be downloaded from the CTEP home page (http://ctep.info.nih.gov).

Please note that this study will not be using separate toxicity scales for acute and late radiation adverse events.

9.3 Response Assessment (RECIST Criteria)

Response will be evaluated in this study using the international criteria proposed by the Response Evaluation Criteria in Solid Tumors (RECIST) Committee JNCI 92(3): 205-216, 2000. See http://ctep.cancer.gov/protocolDevelopment/docs/therasserecistinci.pdf for further details.

9.3.1 Evaluation of Target Lesions

Complete Response (CR): Disappearance of all target lesions. Disappearance of all target lesions. Any pathological lymph nodes (whether target or non-target) must have reduction in short axis to <10 mm (the sum may not be "0" if there are target nodes). Determined by two separate observations conducted not less than 4 weeks apart. There can be no appearance of new lesions.

Partial Response (PR): At least a 30% decrease in the sum of the longest diameter (LD) of target lesions, taking as reference the baseline sum LD. There can be no appearance of new lesions.

Progressive Disease (PD): > 20% increase in the SLD taking as reference the smallest SLD recorded since the treatment started (nadir) and minimum 5 mm increase over the nadir.

Stable Disease (SD): Neither sufficient shrinkage to qualify for PR nor sufficient increase to qualify for PD, taking as reference the smallest sum LD since the treatment started. There can be no unequivocal new lesions.

9.3.2 Evaluation of Non-Target Lesions

Complete Response (CR): Disappearance of all non-target lesions and normalization of tumor marker level. All lymph nodes must be non-pathological in size (< 10 mm short axis).

Incomplete Response/Stable Disease (Non-CR/Non-PD): Persistence of one or more non-target lesion(s) and/or maintenance of tumor marker level above the normal limits.

Progressive Disease (PD): Appearance of one or more new lesions and/or unequivocal progression of existing non-target *lesions*

9.3.3 Evaluation of Best Overall Response

The best overall response is the best response recorded from the start of the treatment until disease progression/recurrence (taking as reference for progressive disease the smallest measurements recorded since the treatment started). The subject's best response assignment will depend on the achievement of both measurement and confirmation criteria.

Time point response: patients with target (+/- non-target) disease.			
		New	Overall
Target lesions	Non-target lesions	lesions	response
CR	CR	No	CR
CR	Non-CR/non-PD	No	PR
CR	Not evaluated	No	PR
PR	Non-PD or not all evaluated	No	PR
SD	Non-PD or not all evaluated	No	SD
Not all			
evaluated	Non-PD	No	NE
PD	Any	Yes or No	PD
Any	PD	Yes or No	PD
Any	Any	Yes	PD

CR = complete response, NE = not evaluable, PD = progressive disease, PR = partial response, SD = stable disease.

Time point response: patients with non-target disease only.			
Non-target lesions	New lesions	Overall response	
CR	No	CR	
Non-CR/non-PD	No	Non-CR/non-PD	
Not all evaluated	No	NE	
UnequivocalPD	Yes or No	PD	

	Any	Yes	PD
--	-----	-----	----

CR = complete response, NE = not evaluable, PD = progressive disease

A 'Non-CR/non-PD' is preferred over 'stable disease' for non-target disease since SD is increasingly used as endpoint for assessment of efficacy in some trials so to assign this category when no lesions can be measured is not advised.

9.3.4 Progression-Free Survival

Progression-free survival (PFS) is defined as the duration of time from start of treatment to time of progression.

9.4 Target lesion assessment guidelines

The longest diameter (LD) for the target lesion (or lesions) will be calculated from the treatment planning CT scan using pulmonary and/or mediastinal windowing and reported as the baseline LD. The baseline LD will be used as a reference by which to characterize the objective tumor.

Local treatment effects in the vicinity of the tumor target may make determination of tumor dimensions difficult. For example, bronchial or bronchiolar damage may cause patchy consolidation around the tumor that over time may coalesce with the residual tumor. In cases in which it is indeterminate whether consolidation represents residual tumor or treatment effect, it should be assumed that abnormalities are residual tumor.

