6.1.4 Target Volumes for Arm A

Definition of the GTV and CTV

The primary tumor and clinically positive lymph nodes seen either on the planning CT (> 1 cm short axis diameter) or pretreatment PET scan (SUV > 3) will constitute the Gross Tumor Volume (GTV). The GTV, strictly defined, does not include motion and hence is identified on a "motionless" image set (e.g., a fast spiral CT or a specific respiratory phase from a 4-D CT). This volume(s) may be disjointed. In the event of a collapsed lobe or lung segment, the use of PET to distinguish tumor from fluid/atelectasis is encouraged. The GTV should be expanded into a Clinical Target Volume (CTV) to account for microscopic infiltration by adding a minimum of 5 mm and a maximum of 10 mm in any direction (at the discretion of the treating physician) with careful attention to trim expansions into normal structures and bone. **Elective treatment of nodal areas is not allowed.**

Definition of the ITV:

The ITV includes the envelope that encompasses the tumor motion for a complete respiratory cycle. The motion quantified from the 4-D scan or real time fluoroscopy will be added to the CTV to constitute the ITV. If the motion is greater than 10-15 mm in any direction, special maneuvers such as abdominal compression, gating, chasing or regimented breath hold should be used to reduce the final motion below 10mm. Thus, expansions will range from 0-10 mm. If it is observed that the tumor has no motion, then the ITV would be identical to the CTV.

Definition of the PTV

The PTV is defined as the ITV with additional margin for setup uncertainties. Daily imaging is used to reposition the patient to minimize setup errors (see Section 6.1.1). The ITV will be expanded by 5 mm in all directions to create the PTV.

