6.2.4 Target Volumes for Arm B

Note: The following definitions are written for Arm B with the assumption that image guidance, adaptive replanning, and motion assessment and control are not utilized as per standard lung radiotherapy practice. However, at the discretion of the treating physician, such methods may be utilized on Arm B as absolutely required for patients randomized for Arm A. If these technologies and techniques are utilized, the Target Volumes should be as described in Section 6.1.4 rather than 6.2.4.

Definition of the GTV and CTV

The primary tumor and clinically positive lymph nodes seen either on the planning CT (> 1 cm short axis diameter) or pretreatment PET scan (SUV > 3) will constitute the Gross Tumor Volume (GTV). The GTV, strictly defined, does not include motion and hence is identified on a "motionless" image set (e.g., a fast spiral CT or a specific respiratory phase from a 4-D CT). This volume(s) may be disjointed. In the event of a collapsed lobe or lung segment, the use of PET to distinguish tumor from fluid/atelectasis is encouraged. The GTV should be expanded into a Clinical Target Volume (CTV) to account for microscopic infiltration by adding a minimum of 5 mm and a maximum of 10 mm in any direction (at the discretion of the treating physician) with careful attention to trim expansions into normal structures and bone. **Elective treatment of nodal areas is not allowed.**

Definition of the ITV:

The ITV includes the envelope that encompasses the tumor motion for a complete respiratory cycle. A minimum of 1 cm in the axial direction and 2 cm in the superior-inferior direction will be added to the CTV to define the ITV. If the motion quantified from the 4-D scan or real time fluoroscopy is greater, additional margin should be added accordingly.

Definition of the PTV

The PTV is defined as the ITV with additional margin for setup uncertainties and may be individualized but should not be less than 0.5 cm or greater than 1.0 added to the ITV to create the PTV.

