6.9 Radiation Adverse Events

Adverse Events will be categorized and graded based primarily on the Common Toxicity Criteria for adverse events Version 4.0 (CTCAE version 4.0) with the exception of changes in pulmonary function tests (see section 6.9.4 below).

Radiotherapy should be interrupted for Grade 4 in-field toxicity and resumed when that toxicity has decreased to Grade ≤ 2 as detailed below. If treatment is interrupted for > two weeks, the patient should be removed from study treatment.

6.9.1 Reversible or permanent alopecia, bone marrow toxicity, skin pigmentation, and esophagitis are expected side effects of radiation therapy. Radiation induced myocarditis or transverse myelitis rarely occur at doses lower than 50 Gy. Radiographic evidence of radiation change and subsequent fibrosis of the lung will occur within lung volume receiving ≥20 Gy, usually within the first six months after initiation of treatment. It is essential to spare as much normal lung as possible in order to avoid symptomatic lung injury.

Adverse Event Monitoring

Adverse event data collection and reporting, which are required as part of every clinical trial, are done to ensure the safety of subjects enrolled in the studies as well as those who will enroll in future studies. Adverse events are reported in a routine manner at scheduled times during a trial. Additionally, certain adverse events must be reported in an expedited manner to allow for optimal monitoring of subject safety and care.

All subjects experiencing an adverse event, regardless of its relationship to study therapy, will be monitored until:

- the adverse event resolves or the symptoms or signs that constitute the adverse event return to baseline or is stable in the opinion of the investigator;
- > there is a satisfactory explanation other than the study therapy for the changes observed; or
- death.

Definitions

An adverse event is defined as any untoward or unfavorable medical occurrence in a human research study participant, including any abnormal sign (for example, abnormal physical exam, imaging finding or clinically significant laboratory finding), symptom, clinical event, or disease, temporarily associated with the subject's participation in the research, whether or not it is considered related to the subject's participation in the research.

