9.6 Other response parameters

- **9.6.1** Time to Local Progression: The time to progression will be measured from the date of study enrollment to the date of documented local progression as determined by clinical exam and imaging studies.
- **9.6.2** Overall Survival: The survival time will be measured from the date of study enrollment to the date of death. All patients will be followed for survival. Every effort should be made to document the cause of death.
- **9.6.3** Progression Free Survival: Progression free survival will be measured from the date of study enrollment to the date occurrence of local or regional progression, distant metastases, or death from any cause.

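### Section 9.4 scores indeterminate consolidation as tumor without limiting this to response, so some radiation change can be counted as local progression and as a PFS event

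*Combined protocol and SAP*

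**What the plan says.** - Section 9.4 warns that "bronchial or bronchiolar damage may cause patchy consolidation around the tumor that over time may coalesce with the residual tumor", and then gives the default: "In cases in which it is indeterminate whether consolidation represents residual tumor or treatment effect, it should be assumed that abnormalities are residual tumor". It stands under target-lesion assessment in general, and nothing confines it to CR or PR.
- Section 9.3.1 defines target-lesion PD as more than a "20% increase in the SLD taking as reference the smallest SLD recorded since the treatment started (nadir) and minimum 5 mm increase over the nadir". No second scan is required. A repeat observation, at least four weeks later, is required only for CR.
- Section 9.3.2 asks for unequivocal progression, but only for non-target lesions. Section 9.3.3 mentions confirmation only for best response.
- Section 6.9.1: "Radiographic evidence of radiation change and subsequent fibrosis of the lung will occur within lung volume receiving ≥20 Gy", usually in the first six months after treatment starts. Appendix II schedules response CTs from month 3.
- Section 9.6.1 ends time to local progression at the "date of documented local progression as determined by clinical exam and imaging studies". Under 9.6.3 and 11.1.2.3, local progression is also a PFS failure. Section 11.5.6 tests both endpoints with a stratified log-rank test.
- No section requires follow-up PET, biopsy, a repeat scan or central image reading before progression is recorded. PET is mentioned for staging and for planning the target, not for follow-up.

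**The concern.** Calling uncertain tissue tumor is cautious when the question is response, because it avoids a false CR or PR. When the question is progression, the same default works the other way and can turn treatment effect into an event. The protocol itself predicts the confounder, at a time that overlaps the first response CTs.

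Time to local progression and PFS are the measures closest to the trial's hypothesis that hypofractionation kills more tumor. If false progressions are equally common in both arms, the comparison is diluted. If they are not, a difference in fibrosis could be reported as a difference in tumor control, or could hide one. Unequal rates are plausible because the arms differ in dose per fraction (4 versus 2 Gy) and, when Arm B is treated without image guidance, in margins.

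**Working it through.** **The plan's own figure.** The 1-year survival rates of 45% and 60% (11.2) give hazards of 0.799 and 0.511, HR 0.640. Schoenfeld events = 4(1.960 + 0.842)² / (ln 0.640)² = 158. With 2 years of uniform accrual and 1 year of follow-up, the mean event probability is 0.700, so N = 158/0.700 = 226; 226/0.95 = 238. The design figure reproduces. It concerns overall survival only, which this point does not touch.

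**How much enlargement makes PD.** A stable 50 mm lesion crosses the threshold once the diameter rises by more than 0.20 × 50 = 10 mm, or just over 5 mm per side. A lesion that has shrunk to 35 mm needs more than 0.20 × 35 = 7 mm in total. The lesion sizes are illustrative. For comparison, margins beyond the GTV per side are:
- Arm A (6.1.4): 5+0+5 = 10 mm to 10+10+5 = 25 mm. The last term is "The ITV will be expanded by 5 mm in all directions to create the PTV".
- Arm B without image guidance (6.2.4): at least 5+10+5 = 20 mm axially and 5+20+5 = 30 mm superior-inferior, from "A minimum of 1 cm in the axial direction and 2 cm in the superior-inferior direction will be added to the CTV".

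This shows only that the threshold can be reached inside treated tissue. It does not give a rate.

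**Effect on the endpoints.** The documents give no false-PD rate, local-progression hazard or PFS median, so all of these are assumed. Simulation for local progression: 113 per arm; deaths at 0.511 (A) and 0.799 (B) per year, treated as censoring; Arm B local hazard 0.40 per year; true HR 0.64 or 1; censoring uniform on 1-6 years; a false PD assigned with probability q at 0.33, 0.60 or 0.85 years if the patient is still at risk; unstratified log-rank; 1,000-2,000 runs per case. The PFS version assumes an Arm B median of 7 months, with 300-1,500 runs. Ranges show separate runs.

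| False PD, A / B | True HR | Local progression: HR, rejections | PFS: HR, rejections |
|---|---|---|---|
| 0 / 0 | 0.64 | 0.63-0.64, 44-46% | 0.64, 89-90% |
| 5% / 5% | 0.64 | 0.66, 41% | 0.64, 89% |
| 10% / 10% | 0.64 | 0.68, 38% | 0.66, 84% |
| 20% / 20% | 0.64 | 0.73, 29-30% | 0.67, 77% |
| 30% / 15% | 0.64 | 0.94, 6% | 0.75, 53% |
| 10% / 5% | 1 | 1.08, 6.1% | 1.03, 5.0% |
| 30% / 15% | 1 | 1.22-1.24, 16-18% | not run |
| 15% / 30% | 1 | 0.81, 16-18% | not run |

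Varying the Arm B local hazard over 0.3-0.6 gives HR 0.69-0.74 at 20%/20%. With no true difference, 20%/10% gives HR 1.11-1.19 and 9-14% rejections. A separate PFS simulation on the plan's accrual pattern, with Arm B medians of 6-12 months and equal rates of 10-30%, gives HR 0.65-0.72, and type I error stays near 5%.

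**Cost of asking for confirmation.** The chance of death before the next scan is 1 − exp(−hazard × interval):
- 3 months: 1 − exp(−0.511 × 0.25) = 12% (A); 1 − exp(−0.799 × 0.25) = 18% (B).
- 4 months: 16% and 23%.
- 6 months: 23% and 33%.

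At the design hazards these losses are not rare, and they differ by arm.

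**The case against.** The strongest reply is that 9.4 is narrower than it looks. It speaks of residual tumor and applies only when the reader cannot tell tumor from treatment effect. Section 6.9.1 says radiographic change will occur; it does not say the change will be indeterminate or will merge with the lesion. A reader who thinks enlargement is probably treatment effect need not use the default. The enlargement must still pass 20% and 5 mm, and 9.6.1 brings in the clinical examination. Section 9.3 also points to external RECIST guidance, which is not available here. All of this stands as a limit on frequency. None of it tells the reader how to keep an indeterminate enlargement from being scored as PD.

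Three stronger readings are tempting, and the documents do not support them.
- A reader might infer that expected fibrosis will routinely be scored as progression. The text shows that it can be, not how often. The largest effects above need assumed rates of 30% versus 15%; at 5% in each arm the change is small.
- A reader might infer from the margins which arm is disadvantaged. Section 6.9.1 ties fibrosis to lung receiving at least 20 Gy, not to the PTV. Expansions are trimmed at normal structures and bone, and Arm B takes Arm A's volumes when image guidance and motion control are used. The direction cannot be predicted.
- A reader might infer a threat to the main result. Overall survival does not depend on image reading. Time to local progression is an objective in 2.2.1 but is missing from the endpoint list in 11.1.2, and its power is only about 45% on these assumptions even without false PD.

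It is also fair to object to replacing the present rule outright with a confirmation rule, because deaths before confirmation would remove true progressions more often in Arm B.

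**Conclusion.** The gap is in the text: the 9.4 default reaches progression, target-lesion PD needs one scan, and the result feeds two secondary measures. It should be closed, but its size is unknown. Over assumed false-PD rates of 5-30%, the effect on time to local progression runs from slight (HR about 0.64 to 0.66 at 5% in each arm) to substantial (about 0.73 at 20% in each arm; about 1.2 with no true difference at 30% versus 15%). PFS is less affected. Equal rates dilute the effect without inflating type I error; unequal rates can bias in either direction. These sizes rest on the assumed rates, local hazard and PFS median. The reading of 9.3.1, 9.4 and 9.6 does not. Overall survival and the 226/238 sample size are unaffected.

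**What to change.** 1. In 9.4, state that the default is intended for scoring response (CR/PR).
2. Add one CRF flag for in-field enlargement judged indeterminate, and define in-field. The volume receiving at least 20 Gy, as named in 6.9.1, would be a natural choice.
3. In 11.5.6, prespecify that time to local progression and PFS are reported under two definitions, and name in advance which one leads:
   - (a) the 9.4 rule as it reads now;
   - (b) flagged enlargement counts as PD only if, on a later scheduled CT, the sum again meets the 9.3.1 threshold (more than 20% and at least 5 mm) relative to the first flagged scan, or if PET or biopsy done for clinical reasons shows tumor. Confirmed PD is dated to the first flagged scan.
4. Under (b), a patient who dies before confirmation has a PFS event at death. For time to local progression, analyse such patients once as events and once as censored, because of the arm difference in early deaths.
5. New lesions and growth outside the irradiated volume remain PD at once.
6. Refer to these definitions in 9.6.1 and 9.6.3. They govern analysis only.

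The cost is one CRF field, wording in three sections and a second analysis, with some cases left unconfirmed. Confirmation is imperfect, since 9.4 itself says consolidation may coalesce over time and so can keep enlarging; that is a reason to report both definitions. The CTs are already scheduled, and no extra readers are needed.
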